### **Rational of the study**

In late December 2019, several local health facilities reported clusters of patients with pneumonia of unknown cause that were epidemiologically linked to a seafood and wet animal wholesale market in Wuhan, Hubei Province, China. It is now confirmed that the etiology of this outbreak is a novel coronavirus, namely, SARS-CoV-2. Of critical importance is rapid and simple diagnostic method to be used in clinical settings to timely inform and refine strategies that can prevent, control, and stop the spread of SARS-CoV-2. The 2019-nCoV IgG/IgM Rapid Test Cassette (Whole Blood/Serum/Plasma) is a qualitative membrane based immunoassay for the detection of IgG and IgM antibodies to SARS-CoV-2 in whole blood, serum or plasma specimen. This test consists of two components, an IgG component and an IgM component. In the IgG component, anti-human IgG is coated in IgG test line region. During testing, the specimen reacts with 2019-nCoV antigen-coated particles in the test cassette. The mixture then migrates upward on the membrane chromatographically by capillary action and reacts with the anti-human IgG in IgG test line region, if the specimen contains IgG antibodies to SARS-CoV-2.

### **Aim of the study**

To validate in a real life study a self diagnostic assay for SARS-CoV-2 with the advantages of high speed, simple operation and low cost, and overcomes the shortcomings of the existing molecular detection methods. Clinical specimens from patients who were suspected of being infected with 2019-nCoV will be used to evaluate the performance of the assay. In parallel, we will also use molecular assays for the detection of the presence of the viral RNA from nasopharyngeal swabs since PCR is currently the gold standard.

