#### Primary endpoints

- 1) To estimate the rate of SARS-CoV-2 positive cancer patients (undergoing chemotherapy, immunotherapy, biological therapy, radiotherapy or experimental treatments or major surgery) and health professionals in a comprehensive cancer center or in a cancer setting. Patients positive are serially tested with SARS-CoV-2 IgM / IgG Rapid Test to evaluate the immune response in IgG negative patients and the reliability of the test in those patients who develop clinical signs of SARS-CoV-2 during the trial.
- 2) To validate the accuracy of self diagnostic assay by confirmation of IgM and/or IgG positive test with the current gold standard RT-PCR for positive nucleic acid detection of new coronavirus from nasopharyngeal swabs.
- 3) To perform on plasma samples multiplex immunoassay protein quantitation related to markers of inflammation and immunity (IL-6, TNF, INF $\gamma$ , IL1, IL-2). 2.5 ml of plasma will be needed.

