### **Study Population**

Patients or health professionals already tested positive for the viral RNA from nasopharyngeal swabs by RT-PCR. Patients or health professional who are suspected of being infected with SARS-CoV-2 in the hospital. Patients who are considered at high risk for infection and eligible for active therapy and major surgery.

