#### **2. Confirmed cases**

Patients or subjects with positive RT-PCR for SARS-CoV-2. On the basis of meeting the criteria for suspected cases, sputum, throat swabs, lower respiratory tract secretions, and other specimens were tested by real-time RT-PCR for positive nucleic acid detection of new coronavirus; or viral gene sequencing was highly homologous with known new coronaviruses. Patients positive are serially tested with SARS-CoV-2 IgM / IgG Rapid Test to evaluate the immune response in IgG negative patients and the reliability of the test in those patients who develop clinical signs of SARS-CoV-2 during the trial.

3. Patients who are considered at high risk for infection and eligible for active therapy and major surgery

- Frailty (age and multiple comorbidities) planned to receive a standard systemic anticancer treatment comprising chemotherapy and/or immunotherapy and/or radiation therapy or to receive an experimental treatment
- Major surgery or surgery after neoadjuvant chemotherapy and or chemo/radiotherapy

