## Statistical Plan

All data recorded will be summarized in tables, graphs and listings. In general, categorical data will be presented using counts and percentages, whilst continuous variables will be presented using the mean, standard deviation, median, minimum, maximum and number of patients.

In tabulations, denominators for calculation of percentages will be taken as the number of non-missing responses.

Primary end-point, the accuracy of tests, will be sensitivity and specificity and they will be calculated for all tests and compared with the appropriate statistical test.

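### The aim evaluates the assay in suspected patients, but the accuracy analysis is neither restricted to them nor split by entry group, so the headline sensitivity and specificity are not assured to describe them

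*Combined protocol and SAP*

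**What the plan says.** Four parts of the document bear on this point.

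- **Population for evaluating the assay.** Aim of the study: "Clinical specimens from patients who were suspected of being infected with 2019-nCoV will be used to evaluate the performance of the assay". The same section says molecular assays on swabs will be used in parallel and names no subgroup for them.
- **People enrolled.** Study Population lists three groups. The first is "Patients or health professionals already tested positive for the viral RNA from nasopharyngeal swabs by RT-PCR". The second consists of patients and staff in whom infection is suspected. The third is "Patients who are considered at high risk for infection and eligible for active therapy and major surgery". Item 3 of the Inclusion Criteria defines the last group by frailty with planned anticancer treatment, or by major surgery. It asks for no symptom and no contact. The front page gives 1000 participants, 200 per site, with no split by entry group.
- **Accuracy analysis.** Statistical Plan, on sensitivity and specificity: "they will be calculated for all tests and compared with the appropriate statistical test". No analysis set, restriction or stratification follows.
- **Who gets RT-PCR.** Under Clinical considerations, suspected patients are proposed for RT-PCR by clinical judgement whatever the serology. Beyond that, RT-PCR is assured only for IgM positives. Item 2 of the Primary endpoints likewise frames validation as "by confirmation of IgM and/or IgG positive test with the current gold standard RT-PCR".

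**The concern.** The plan never connects the population in the aim to the calculation in the Statistical Plan. With no analysis set, the mix of people recruited decides what the headline figures mean, and that mix is not fixed anywhere.

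The two added groups act differently. A person enrolled because RT-PCR was already positive can enter only the sensitivity denominator, if that result serves as the reference. This is selection on the reference result. It is settled at entry, so clarifying test timing alone would not remove it. A high-risk person of whom no suspicion is required bears mainly on specificity, and the effect depends on whether cassette negatives in that group also have RT-PCR.

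At stake is the claim of a real-life validation. A pooled figure could be quoted as performance in suspected patients when a large part of it comes from people whose diagnosis was already known, or from people tested before treatment without suspicion.

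**Working it through.** **Nothing in the plan to reproduce.** The enrolment of 1000 has no expected accuracy or precision behind it. The only accuracy figures in the document are those in the Performance study section (IgG 100% sensitivity and 98.0% specificity; IgM 85.0% and 96.0%). They are not broken down by the entry groups used here, so they cannot supply the inputs. Every group share and group-specific accuracy below is an assumption, chosen to show direction and scale.

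**Step 1: sensitivity.** Let w be the share of RT-PCR positives who were already confirmed at entry.

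Pooled sensitivity = w × (sensitivity in confirmed) + (1 − w) × (sensitivity in suspected)

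| Confirmed / suspected | w = 0.25 | w = 0.50 | w = 0.75 |
|---|---|---|---|
| 95% / 70% | 76.25% | 82.5% | 88.75% |
| 95% / 85% | 87.5% | 90.0% | 92.5% |
| 85% / 95% | 92.5% | 90.0% | 87.5% |

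For example, 0.50 × 0.95 + 0.50 × 0.70 = 0.825. The shift is upward if confirmed entrants are easier to detect, downward if they are harder, and zero if the groups are alike.

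**Step 2: a worked mix of 1000.** Assume 200 already confirmed, 400 suspected of whom 30% are RT-PCR positive, and 400 high-risk of whom 2% are positive.

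- RT-PCR positives: 200 + 120 + 8 = 328. Confirmed entrants are 200/328 = 61% of them.
- RT-PCR negatives: 280 + 392 = 672. High-risk entrants are 392/672 = 58% of them.
- Assumed sensitivity: 95% in confirmed, 70% in the other two groups.
- Assumed specificity: 90% in suspected, 98% in high-risk.

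Pooled sensitivity with RT-PCR in everyone = (190 + 84 + 5.6)/328 = 279.6/328 = 85.2%, against 70% in suspected patients.

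**Step 3: specificity under two readings of who gets RT-PCR.**

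- *Everyone*, taking the parallel testing in the aim at its widest: (0.90 × 280 + 0.98 × 392)/672 = (252 + 384.16)/672 = 94.7%. This is above the 90% in suspected patients.
- *High-risk entrants only if cassette positive*, following Clinical considerations: they add 0.02 × 392 = 7.84 false positives and no true negatives. Specificity = 252/(280 + 7.84) = 87.5%. This is below 90%.

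Under the second reading, specificity in the high-risk group alone is 0/(0 + 7.84) = 0% by construction. Pooled sensitivity becomes 279.6/(200 + 120 + 5.6) = 85.9%, because that group's false negatives are never seen.

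**Step 4: what restricting to suspected patients costs.** Approximate 95% half-width = 1.96 × √(p(1 − p)/n).

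- Suspected only: 1.96 × √(0.70 × 0.30/120) = 8.2 points.
- Pooled: 1.96 × √(0.852 × 0.148/328) = 3.8 points, but around a different quantity.

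**The case against.** Four objections have weight.

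**Pooling over everyone is not stated.** The phrase "they will be calculated for all tests" may refer to the IgG and IgM components, which the Performance study section reports separately, and the aim may be meant to supply the missing population. This stands: pooling over all participants is the default reading of a silent plan. On either reading, though, the Statistical Plan names no accuracy population.

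**Confirmed cases may themselves be suspects.** Part of that criterion reads "On the basis of meeting the criteria for suspected cases", and sensitivity is conditional on RT-PCR positivity in any case. Adding RT-PCR positives who once met the suspect criteria need not bias it. This stands in part. The sentence just before it, and the Study Population section, admit RT-PCR positives without that condition, and such people enter with the diagnosis already known.

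**The direction for specificity is not settled.** This stands in full, as step 3 shows.

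**The inputs are invented.** This also stands. Nothing in the document supports a 25-point gap in sensitivity, so the figures are illustrations only.

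A reader might go further and infer that neither figure describes suspected patients, that the hard-to-classify suspects are left out, or that both measures must look better than they are. The document does not support this. Suspected patients are enrolled under criterion 1 and can contribute to both denominators, so at most the figures are diluted. Specificity can also fall.

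**Conclusion.** The concern holds as a gap between the stated aim and the analysis. The aim names suspected patients, enrolment adds two other groups, and the accuracy calculation is neither restricted nor stratified. The headline sensitivity and specificity are therefore not assured to describe suspected patients.

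Sensitivity would probably shift upward if already-confirmed entrants are easier to detect. Under the assumptions in step 1, with confirmed entrants at 95%, the rise is 2.5 to 7.5 points from a base of 85%, and about 6 to 19 points from a base of 70%. Specificity could move up or down: +4.7 or −2.5 points from 90% in the worked mix. The true size is unknown, because the plan gives neither the group shares nor the accuracies within groups. If the groups perform alike and RT-PCR does not depend on the cassette result, pooling changes nothing.

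This is a cheap improvement. It does not show that the planned figures will be wrong.

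**What to change.** Amend the Statistical Plan as follows.

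1. **Primary accuracy set.** Participants enrolled under suspected-case criterion 1 whose RT-PCR result was unknown when the cassette was read, and who have a paired RT-PCR obtained regardless of the cassette result. Report how many suspected entrants fall outside the set for want of such a pair, since Clinical considerations leaves their RT-PCR to clinical judgement.
2. **Already-confirmed entrants.** A separate row, sensitivity only, not pooled into the headline.
3. **High-risk entrants.** A separate row. Give specificity only for those whose RT-PCR was done irrespective of the cassette result. For the rest, give only the proportion of cassette positives confirmed by RT-PCR, since specificity has no meaning where negatives are not verified.

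The cost is wording in the Statistical Plan, plus a record of each participant's entry group, of whether the RT-PCR result was known at the reading, and of why RT-PCR was done. No data are discarded. The downside is fewer RT-PCR positives behind the headline sensitivity and so a wider interval: about ±8.2 instead of ±3.8 points in the worked mix.

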#### Primary endpoints

- 1) To estimate the rate of SARS-CoV-2 positive cancer patients (undergoing chemotherapy, immunotherapy, biological therapy, radiotherapy or experimental treatments or major surgery) and health professionals in a comprehensive cancer center or in a cancer setting. Patients positive are serially tested with SARS-CoV-2 IgM / IgG Rapid Test to evaluate the immune response in IgG negative patients and the reliability of the test in those patients who develop clinical signs of SARS-CoV-2 during the trial.
- 2) To validate the accuracy of self diagnostic assay by confirmation of IgM and/or IgG positive test with the current gold standard RT-PCR for positive nucleic acid detection of new coronavirus from nasopharyngeal swabs.
- 3) To perform on plasma samples multiplex immunoassay protein quantitation related to markers of inflammation and immunity (IL-6, TNF, INF $\gamma$ , IL1, IL-2). 2.5 ml of plasma will be needed.

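### Primary endpoint 1 asks for a rate of SARS-CoV-2 positives, but the cohort pools known RT-PCR positives, suspected cases and high-risk patients, and the analysis does not separate them

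*Combined protocol and SAP*

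**What the plan says.** Primary endpoints, item 1, sets out "To estimate the rate of SARS-CoV-2 positive cancer patients" "and health professionals in a comprehensive cancer center or in a cancer setting". It names no defining test, denominator or entry group. It also mentions serial testing and patients who develop clinical signs during the trial, but gives no time window for the rate.

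Study Population and the Inclusion Criteria admit three groups:

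- Known positives: "Patients or health professionals already tested positive for the viral RNA from nasopharyngeal swabs by RT-PCR". The criteria repeat this as "Patients or subjects with positive RT-PCR for SARS-CoV-2" and build the confirmed group on the suspected-case criteria, so the two overlap.
- Suspected cases: "Patients or health professional who are suspected of being infected with SARS-CoV-2 in the hospital".
- High-risk patients: "Patients who are considered at high risk for infection and eligible for active therapy and major surgery".

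The opening study details give 1000 participants, 200 per site, with no split by group. The Statistical Plan offers general counts and percentages, takes non-missing responses as the denominator, and names sensitivity and specificity as the primary end-point. It has no specific analysis of the endpoint 1 rate.

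Three sections bear on who has RT-PCR. The Aim of the study says "In parallel, we will also use molecular assays for the detection of the presence of the viral RNA from nasopharyngeal swabs". Primary endpoint 2 relies on "confirmation of IgM and/or IgG positive test with the current gold standard RT-PCR". Clinical considerations requires a confirmatory RT-PCR in IgM-positive patients. It also proposes RT-PCR, at clinical judgement, to patients with epidemiological history and/or clinical manifestations, whatever their serology.

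**The concern.** One entry group is positive by selection, a second is chosen on suspicion of infection, and the third is chosen on risk and planned treatment. A single percentage over all of them is a weighted average whose weights are set by recruitment. Two centres with the same infection burden could report very different rates, and the result could be read as the frequency of infection in a cancer setting.

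For health professionals the problem is sharper. The high-risk category is for patients only, so staff enter only because they are suspected or confirmed. Endpoint 1 nevertheless names them.

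A secondary issue is that 'positive' could mean RT-PCR, IgM, IgG or either antibody. These give different rates in a low-prevalence group, and they call for different denominators.

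**Working it through.** **Plan's own figures.** 1000/200 = 5 sites. No expected rate, precision or power is given, so there is no statistical basis for the 1000 to reproduce.

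**1. Dependence on mix.** Let c be the share of known positives, s the share of suspected cases, and ps and ph the infected proportions among suspected and high-risk participants. Known positives count as 100% if positive means RT-PCR. The pooled rate is p = c + ps·s + ph·(1 − c − s). The documents give none of these values. Assumed: ps = 0.30, ph = 0.03, and s = 0.40 at the start.

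- c = 0.10: 0.10 + 0.30×0.40 + 0.03×0.50 = 23.5%.
- c = 0.20, suspected displaced (s = 0.30): 0.20 + 0.09 + 0.015 = 30.5%.
- c = 0.20, both groups shrink in proportion (s = 0.40×0.8/0.9 = 0.356): 0.20 + 0.107 + 0.013 = 32.0%.
- c = 0.20, high-risk displaced (s = 0.40): 0.20 + 0.12 + 0.012 = 33.2%.

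The shift is 7.0 to 9.7 points. The 95% half-width, 1.96·√(p(1 − p)/1000), is 2.6 points at 23.5% and 2.9 at 30.5% and 33.2%.

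Range: with ps from 10% to 50% and ph from 1% to 10%, the shift is 0.1·(1 − ps) = 5.0 to 9.0 points if suspected cases are displaced, and 0.1·(1 − ph) = 9.0 to 9.9 points if high-risk patients are. Half-widths are 2.2 to 3.1 points.

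**2. Is excluding known positives enough?** Take ps = 30% and ph = 5%, and compare confirmed/suspected/high-risk mixes of 5/25/70% and 50/40/10%. Without the known positives, the rates are (0.075 + 0.035)/0.95 = 11.6% and (0.12 + 0.005)/0.50 = 25.0%. Suspected and high-risk participants must be separated as well.

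**3. Definition of positive, high-risk group, 3% infected (assumed).** Sensitivities (IgG 100%, IgM 85%) and specificities with their limits come from Tables 1 and 2 of the Performance study. The summary sentence below those tables gives 98.6% and 92.7%, which match neither table's sensitivity and specificity; the tables are used here. The apparent rate is 0.03·sensitivity + 0.97·(1 − specificity). For either antibody, sensitivity is 100% and false positives are taken as independent.

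| Specificity used (IgG; IgM) | IgG | IgM | Either |
|---|---|---|---|
| Upper limits (99.9%; 99.5%) | 3.1% | 3.0% | 3.6% |
| Point estimates (98.0%; 96.0%) | 4.9% | 6.4% | 8.7% |
| Lower limits (89.4%; 86.3%) | 13.3% | 15.8% | 25.2% |

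For example, either antibody at the point estimates: 0.03 + 0.97×(1 − 0.98×0.96) = 8.7%. If the false positives overlap fully it is 0.03 + 0.97×0.04 = 6.9%. An RT-PCR definition with everyone tested gives 3.0%, taking RT-PCR as the reference.

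**4. Denominator.** Under Clinical considerations, high-risk patients with IgM positivity, contact history or symptoms are more likely to be swabbed than the rest. If unswabbed patients count as missing, the non-missing rule puts an enriched subset in the denominator, so an RT-PCR rate is likely to be too high. The documents do not allow the size to be derived.

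**The case against.** Every share and infection rate above is assumed, and the Aim and the Statistical Plan centre on test accuracy, so the rate might be treated as incidental description. The first part is true, but the dependence on mix is algebraic. It becomes small only if few known positives enrol and the other two groups have similar rates, which nothing in the plan ensures. As to the second, item 1 is listed first among the primary endpoints. Known positives remain useful for accuracy and serial response; the difficulty is confined to the rate.

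Four stronger readings are tempting and are not supported:

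- *That the pooled rate mainly reflects recruitment.* In the base case known positives supply 0.10/0.235 = 43% of positives. The dependence is material, but the documents give no mix from which to say it dominates.
- *That an antibody definition more than doubles the high-risk rate.* It does at some of the point estimates, but not at the upper specificity limits.
- *That RT-PCR depends only on the cassette result.* Clinical considerations proposes it on history or symptoms irrespective of serology. Swabbing IgM positives alone would give 0.0255/0.0643 = 39.7% for a true 3%, but that supposes nobody with contact or symptoms is swabbed, which is not the plan.
- *That the three sections set three conflicting swab rules.* The Aim speaks of suspected patients, which is compatible with Clinical considerations. The clear mismatch is IgG-only positives, whom endpoint 2 covers and the IgM confirmation rule does not. There is also a difference between RT-PCR proposed at clinical judgement and molecular testing stated as something that will be done.

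**Conclusion.** The point holds. A single rate under endpoint 1 would not be interpretable as infection frequency in a cancer setting. Under the stated assumptions, a 10-point rise in the share of known positives moves it by 7.0 to 9.7 points, and by 5.0 to 9.9 points over the wider range, against a half-width of about 3 points or less. No general rate for health professionals can be obtained, because of how they enter.

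The undefined meaning of 'positive' is a secondary point of uncertain size: from almost no effect to a several-fold one, depending on where specificity lies within the plan's own intervals. Inflation from the non-missing rule is likely in direction and unquantified in size.

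**What to change.** 1. Record the entry group at eligibility, with a hierarchy for overlaps: RT-PCR positive before entry, then suspected, then high-risk.
2. Report the endpoint 1 rate with a 95% confidence interval separately by entry group, and by patient or health professional. Give no pooled centre-wide rate, and describe the results as applying to those enrolled.
3. State what 'positive' means and over what window (baseline, or cumulative to a stated date).
   - If it is newly detected RT-PCR infection: exclude those RT-PCR positive before entry from numerator and denominator, keeping them for accuracy and serial response. Use all remaining enrolled participants in the group as the denominator, show the number tested, and label the rate a lower bound where testing is incomplete.
   - If it is seropositivity: report prior positives as their own stratum rather than dropping them, use all participants with a valid cassette result, and label the rate seropositivity.
4. Reconcile the Aim of the study, primary endpoint 2 and Clinical considerations on who has RT-PCR.

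Cost: items 1 to 3 need wording and one data field, with no new participants or tests. Item 4 could change the number of swabs, depending on how the sections are reconciled. The price is a narrower claim, a lower headline rate and smaller denominators. For illustration, 400 suspected participants at 30% give ±1.96·√(0.3×0.7/400) = ±4.5 points; 400 high-risk patients at 3% give ±1.7 points (Wilson interval for 12/400: 1.7% to 5.2%).

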**Interpretation of the results:**

**IgG POSITIVE:**\* Two colored lines appear. One colored line should always appear in the control line region (C) and another line should be in the IgG line region.

**IgM POSITIVE:**\* Two colored lines appear. One colored line should always appear in the control line region (C) and another line should be in the IgM line region.

**IgG and IgM POSITIVE:**\* Three colored lines appear. One colored line should always appear in the control line region (C) and two test lines should be in the IgG line region and IgM line region.

\*NOTE: The intensity of the color in the test line regions may vary depending on the concentration of 2019-nCoV antibodies present in the specimen. Therefore, any shade of color in the test line region should be considered positive.

**NEGATIVE:** One colored line appears in the control line region (C). No line appears in the IgG region and IgM region.

**INVALID:** Control line fails to appear. Insufficient specimen volume or incorrect procedural techniques are the most likely reasons for control line failure. Review the procedure and repeat the test with a new test. If the problem persists, discontinue using the test kit immediately and contact your local distributor.

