## Performance study

### ***Accuracy, specificity, sensitivity and correlation***

The 2019-nCoV IgG/IgM Rapid Test Cassette (Whole Blood/Serum/Plasma) was compared with a leading commercial PCR; the results show that 2019-nCoV IgG/IgM Rapid Test Cassette (Whole Blood/Serum/Plasma) has a high sensitivity and specificity. Results for IgG and IgM are shown in Table 1 and 2 respectively.

*Table 1: Performance of IgG specimen*

Method		PCR		Total result
Rapid test cassette	Results	Positive	Negative	
	Positive	20	1	21
	Negative	0	49	49
Total result		20	50	70

Specificity = 98.0% (95%CI: 89.4%~99.9%);

Sensitivity = 100% (95%CI: 86.0%~100%);

Accuracy = 98.6% (95%CI: 92.3%~99.96%).

*Table 2: Performance of IgM specimen*

Method		PCR		Total result
Rapid test cassette	Results	Positive	Negative	
	Positive	17	2	19
	Negative	3	48	51
Total result		20	50	70

Specificity = 96.0% (95%CI: 86.3%~99.5%);

Sensitivity = 85.0% (95%CI: 62.1%~96.8%);

Accuracy = 92.9% (95%CI: 84.1%~97.6%).

The 2019-nCov IgG/IgM Rapid Test Cassette (Whole Blood/Serum/Plasma) products have been compared with a commercial PCR using clinical specimen. The results show that the relative sensitivity of the 2019-nCov IgG/IgM Rapid Test Cassette (Whole Blood/Serum/Plasma) is 98.6% and the relative specificity is 92.7%.

Refer to data on investigator brochure for other technical data related to interference and cross-reactivity.

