## Clinical considerations

All patients with epidemiologic history and/or clinical manifestations suspected for COVID will be proposed, according to the clinical judgement, for RT-PCR test for positive nucleic acid detection, irrespective of serological evidence.

All patients tested as IgM positive will have a confirmatory real-time RT-PCR test for positive nucleic acid detection of new coronavirus on sputum, throat swabs, lower respiratory tract secretions, and other specimens.

The 2019-nCov IgG/IgM Rapid Test Cassette (Whole Blood/Serum/Plasma) will be repeated in patients IgM positive for confirming the subsequent IgG positivity.

The tests will be performed locally in each hospital laboratory.

The ASST of Cremona laboratory could perform:

- [name], UO Laboratorio Analisi – ASST di Cremona: SARS-CoV-2 IgG/IgM Rapid Test Cassette (Whole Blood/Serum/Plasma) also for other sites. 1 ml of plasma will be needed;
- [name] SMeL849 – ASST di Cremona: *multiplex* immunoassay protein quantitation related to markers of inflammation and immunity (IL-6, TNF, INF $\gamma$ , IL1, IL-2, ect). 2.5 ml of plasma will be needed.

The lab responsible person in Milano IEO is:

Dr.ssa [name]  
Divisione di Medicina di Laboratorio  
Istituto Europeo di Oncologia

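### Endpoint 1's crude positivity rate pools people enrolled because they were already RT-PCR positive, so it partly reflects recruitment; the defining test and denominator also need stating

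*Combined protocol and SAP*

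**What the plan says.** All references are to the combined protocol and SAP.

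- **Endpoint.** Primary endpoints, item 1: "To estimate the rate of SARS-CoV-2 positive cancer patients" and health professionals. The sentence names no test.
- **Who is enrolled.** Study Population lists three groups: people who already have a positive RT-PCR, people suspected of infection, and high-risk patients due for active therapy or major surgery. Inclusion criterion 2 (Confirmed cases) opens with "Patients or subjects with positive RT-PCR for SARS-CoV-2".
- **Analysis.** Under Statistical Plan, "categorical data will be presented using counts and percentages", with non-missing responses as denominators. That section treats test accuracy as the primary end-point. It gives the endpoint 1 rate no case definition, confidence interval or stratification.
- **Meaning of 'positive'.** Under Interpretation of the results, "any shade of color in the test line region should be considered positive". Under Clinical considerations, the cassette "will be repeated in patients IgM positive for confirming the subsequent IgG positivity". The endpoint 1 sentence on serial testing of positives also appears under Confirmed cases, which are defined by RT-PCR.
- **Who is swabbed.** Clinical considerations: "All patients tested as IgM positive will have a confirmatory real-time RT-PCR test". Suspected cases are offered RT-PCR on clinical judgement, and IgG-only positives are not mentioned. Primary endpoint 2 refers to "confirmation of IgM and/or IgG positive test with the current gold standard RT-PCR".

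**The concern.** A rate estimates how common infection is only if people enter the denominator without regard to the outcome. Here one of the three entry routes is the outcome itself, at least on the RT-PCR reading. Two sites with the same underlying infection rate would report different figures if one recruited more known positives, and the pooled figure could not be compared with any other centre.

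Two further gaps make the number harder to read. First, the text does not fix the test behind 'positive', or whether current or past infection is meant, so two analysts could follow the plan and count differently. Second, RT-PCR is not clearly done on everyone. Under the non-missing rule an RT-PCR percentage would by default be taken over those swabbed, who are a selected group.

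**Working it through.** **1. Recruitment mix.** Planned enrolment is 1000 (200 per site, so 1000/200 = 5 sites). The documents give neither the number of known positives, K, nor the rate p among everyone else, so both are assumptions. If every known positive counts as positive:

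pooled rate = [K + p(1000 − K)]/1000, and its excess over p is (K/1000)(1 − p).

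| K | p | Pooled rate |
|---|---|---|
| 0 | 5% | 50/1000 = 5.0% |
| 50 | 5% | (50 + 47.5)/1000 = 9.75% |
| 100 | 5% | (100 + 45)/1000 = 14.5% |
| 200 | 5% | (200 + 40)/1000 = 24.0% |
| 100 | 2% | (100 + 18)/1000 = 11.8% |
| 100 | 10% | (100 + 90)/1000 = 19.0% |

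The excess does not depend on choosing RT-PCR as the definition. On the IgM line alone, with the tabulated sensitivity of 85%, 100 known positives would still contribute about 85 positives.

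**2. The plan's accuracy figures.** Performance study, Tables 1 and 2, give IgG specificity 49/50 = 98.0% (exact 95% CI 89.4–99.9) and IgM specificity 48/50 = 96.0% (86.3–99.5). Both reproduce. IgG sensitivity is 20/20 and IgM sensitivity 17/20 = 85.0%. For either line positive, sensitivity is 20/20. Specificity is 47/50 = 94% if the one IgG and two IgM false positives are different people, and 48/50 = 96% if they overlap. This assumes that both tables use the same 70 specimens.

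**3. Cassette positivity against RT-PCR-referenced prevalence p.** Apparent rate = Se·p + (1 − Sp)(1 − p). For either line, p is again an assumption:

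| p | Apparent rate (Sp 96% to 94%) | Ratio to p |
|---|---|---|
| 5% | 8.8–10.7% | 1.76–2.14 |
| 10% | 13.6–15.4% | 1.36–1.54 |
| 20% | 23.2–24.8% | 1.16–1.24 |
| 50% | 52–53% | 1.04–1.06 |

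For example, at 5% with Sp 94%: 0.05 + 0.06 × 0.95 = 0.107. With only 50 negatives, the 95% CI for specificity alone moves the ratio at 5% from about 1.1 to 4.1.

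If IgM positives are settled by RT-PCR, at most 1/50 IgG-only false positives remain. The ratio at 5% is then between 1.00 and (0.05 + 0.02 × 0.95)/0.05 = 1.38.

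**4. RT-PCR positivity over those swabbed.** Suppose that in a stratum with p = 5% only IgM positives are swabbed. True positives among them are 0.05 × 0.85 = 0.0425, and all IgM positives are 0.0425 + 0.04 × 0.95 = 0.0805. The rate over those swabbed is 0.0425/0.0805 = 53%, more than ten times the truth. Over the whole stratum it is 4.25%, slightly below 5% because infected IgM negatives are missed.

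**The case against.** **Known positives are needed.** They supply the sensitivity estimate for endpoint 2, and the Statistical Plan treats accuracy as the primary end-point. That stands for endpoint 2. It does not justify counting the same people in a rate that the protocol lists first among its primary endpoints.

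**'Positive' probably means RT-PCR.** The serial-testing sentence recurs under Confirmed cases, and the protocol calls RT-PCR the gold standard. Clinical considerations says IgM positive when it means the cassette. The text does lean this way without settling it. On this reading cassette false positives do not enter the rate, but the recruitment problem remains in full.

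**A reader might infer that the reported rate will be about double the true one.** The documents do not support that as a general statement. It needs an either-line cassette definition, no use of the confirmatory RT-PCR, and a prevalence of roughly 4–6%, a figure the documents do not give. Confirmed and suspected cases raise the cohort's prevalence. A low rate is plausible mainly among high-risk patients. Study Population does not list health professionals in that group; they enter as already positive or suspected. A cassette-positive, RT-PCR-negative person may also have had past infection, so calling the result false presumes that current infection is the target.

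**Two obvious remedies fail.** RT-PCR positives over those swabbed is open to the bias in step 4 of the working. A Rogan-Gladen correction using this study's RT-PCR-referenced accuracy returns the sample RT-PCR proportion if everyone is swabbed, and inherits the selection if not. Aim of the study does speak of molecular assays in parallel. If that means everyone is swabbed, the denominator problem disappears, but Clinical considerations reads otherwise.

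**Conclusion.** The point holds in this form: the planned crude rate is partly set by how many known RT-PCR positives are recruited, whichever test defines 'positive'. The excess is (K/1000)(1 − p), which is 9.5 percentage points with an assumed 100 known positives and 5% in the rest. The actual size cannot be known from the documents, because no mix is planned or stated.

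The undefined test and the selective swabbing are real but secondary. Cassette positivity could be about 1.8–2.1 times the RT-PCR-referenced prevalence at an assumed 5%, 1.4–1.5 times at 10%, and under 1.25 times at 20% or more. These ratios rest on error-free RT-PCR as reference, the same specimens in both tables, and specificity from 50 negatives. They describe what a separate cassette rate might show. They do not show that endpoint 1 will be reported at double its true value.

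**What to change.** In the Statistical Plan, with matching wording in Primary endpoints:

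1. Exclude participants enrolled because already RT-PCR positive from the numerator and denominator of the endpoint 1 rate. Keep them for the accuracy endpoint.
2. Report the rate with 95% confidence intervals by enrolment route (suspected, high-risk), and separately for cancer patients and health professionals.
3. State which test or sequence defines 'positive', and whether current or past infection is estimated.
4. Report RT-PCR positivity over all eligible participants in the stratum, with the number swabbed alongside. Where swabbing is incomplete, read it as a lower bound.
5. Report cassette positivity as a separate rate with a note on specificity. Any correction should use accuracy estimates not taken from a selectively swabbed subset, and its interval should carry their uncertainty.
6. Reconcile endpoint 2, which refers to RT-PCR confirmation of IgM and/or IgG positives, with Clinical considerations, which requires it only for IgM positives.

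The cost is a few lines of text, the enrolment route recorded for each participant, and smaller denominators. At a given 5% rate, the approximate half-width 1.96·√[0.05 × 0.95/n] goes from 1.35 percentage points at n = 1000 to 1.42 at n = 900, and to 3.0 in a stratum of 200 (stratum sizes assumed).
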